5.2.4. Right censored Data

Not applicable.

5.2.5. Visit-specific censored Data

Data from visit x will be censored for the PPS analysis under the following conditions.

| Code | Condition under which the code is used |
|-------|---|
| 112.x | Obvious deviation from Laboratory Manual or error in laboratory data at Day x |
| 270.x | Did not comply with blood draw schedule at Day x |

5.3. Important protocol deviation not leading to elimination from per-protocol analysis set

Not applicable.

6. STATISTICAL ANALYSES

Note that standard data derivation rule and stat methods are described in annex 1 and will not be repeated below.

6.1. Demography

6.1.1. Analysis of demographics/baseline characteristics planned in the protocol

Descriptive statistics (mean, standard deviation, median, minimum and maximum) for age, height and weight at enrolment will be calculated overall and by study group.

| | |
|--|---|
| Statistical Analysis Plan |  GlaxoSmithKline |
| Study alias & e-track number(s): V59 77 (205352) | |
| Version: 1 | Date: 19-09-2016 |

Distributions of subjects by sex, race and ethnic origin will be summarized overall and by study group.

6.1.2. Additional considerations

The frequencies and percentages of subjects with medical history will be presented by MedDRA system organ class and preferred term, by study group and overall.

Medical history and demographic data will be tabulated for the All Enrolled, PPS (Day 29) and Overall Safety set.

6.2. Exposure

6.2.1. Analysis of exposure planned in the protocol

Subjects will be analyzed to the extent that they were exposed to study vaccines and according to the available safety data for the subject during any study period. Subjects who withdraw early or who are lost to follow-up will be removed from the summary table denominator for the time period in which they have no available safety data collected.

6.2.2. Additional considerations

The frequencies and percentages of subjects with vaccination will be summarized overall and by study group. Data will be tabulated for the All Enrolled Set.

6.3. Immunogenicity

6.3.1. Analysis of immunogenicity planned in the protocol

The analysis population to be used for the primary objectives is the PPS (Day 29). Analyses of primary objectives will be repeated on the FAS (Day 29) to assess robustness of results. Analyses of secondary immunogenicity will be based on the PPS and repeated on the FAS.

Missing immunogenicity values are assumed MCAR (Missing Completely At Random) and therefore may not contain information that impact the result of the analysis (i.e., not informative). Imputation methods will therefore not be used.

Statistical Analysis Plan

| | | |
|--|------------|------------------|
| Study alias & e-track number(s): V59 77 (205352) | Version: 1 | Date: 19-09-2016 |
|--|------------|------------------|

 GSK GlaxoSmithKline

The hSBA titers at each visit will be logarithmically transformed (base10) to obtain approximately normally distributed data.

For comparison of percentages and GMT ratios, unadjusted estimates will be obtained along with adjusted estimates from regression models to account for potential baseline imbalance between study groups. For each *N. meningitidis* serogroup A, C, W and Y, unadjusted GMTs will be calculated, with their associated two-sided 95% CIs, by exponentiating the corresponding log-transformed means and their 95% CIs. Adjusted GMTs will be obtained from Analysis of Covariance (ANCOVA) models.

Seroresponse (Day 4, Day 6, and Day 29)

The percentage of subjects with seroresponse and associated two-sided 95% Clopper-Pearson CIs will be computed by group (Menveo-Menveo, Menactra-Menveo, the Naïve and the pooled [Menveo-Menveo and Menactra-Menveo] groups) and *N. meningitidis* serogroups A, C, W and Y test strains. Differences in percentages and associated 95% CIs between study groups will be calculated using the Miettinen & Nurminen score method.

In a descriptive fashion - using the difference in percentages and 95% CIs - each of the previously vaccinated groups (individually and pooled [Menveo-Menveo and Menactra-Menveo]) will be compared to the naïve group. Also the two previously vaccinated study groups will be compared to each other.

As sensitivity analyses, the difference in percentages will also be obtained from a log-linear model adjusting for pre-vaccination titer.

Percentage of Subjects With hSBA titer \geq 8 and \geq 16 (Day 1, Day 4, Day 6, and Day 29)

For each study group and in the pooled group (Menveo-Menveo and Menactra-Menveo), the percentage of subjects with hSBA titer ≥ 8 and ≥ 16 and associated two-sided 95% Clopper-Pearson CIs will be computed by the *N. meningitidis* serogroups A, C, W and Y test strains on Day 1, Day 4, Day 6 and Day 29 (as applicable, depending on blood draw schedule).

Differences in percentages and associated 95% CIs between study groups will be calculated using the Miettinen & Nurminen score method.

| Statistical Analysis Plan | |  GSK GlaxoSmithKline |
|--|------------------|---|
| Study alias & e-track number(s): V59 77 (205352) | Version: 1 | |
| | Date: 19-09-2016 | |

In a descriptive fashion - using the difference in percentages and 95% CIs - the previously vaccinated groups (individually and pooled [Menveo-Menveo and Menactra-Menveo]) will be compared to the naïve group. Also the two previously vaccinated groups will be compared to each other.

As sensitivity analyses, the difference in percentages will also be obtained from a log-linear model adjusting for pre-vaccination titer.

Between-group Ratios of GMTs (Adjusted and Unadjusted)

The between-group ratio of hSBA GMTs and corresponding 95% CI, at each of Visit Day 1 (Persistence), Day 4, Day 6 and Day 29 against each *N. meningitidis* serogroups A, C, W and Y test strains will be obtained by exponentiating the mean between-group differences in log-transformed titers and the corresponding 95% CIs at each of the timepoints specified.

Additionally, adjusted ratio of GMTs will be obtained from ANCOVA models including pre-vaccination titer as factors in the model.

The previously vaccinated groups (individually and pooled [Menveo-Menveo and Menactra-Menveo]) will be compared to the naïve group at each timepoint – descriptively – using the ratios of GMTs.

The two previously vaccinated groups will be compared at each timepoint using GMT ratios.

Within-group GMRs (Adjusted and Unadjusted)

Within each study group and for each serogroup, GMRs will be calculated, as applicable, at:

- Visit Day 4 versus at Visit Day 1;
- Visit Day 6 versus at Visit Day 1; and
- Visit Day 29 versus at Visit Day 1.

The unadjusted GMRs and 95% CIs will be constructed by exponentiating the mean within-group differences in log-transformed titers and the corresponding 95% CIs.

| | |
|--|------------------|
| Statistical Analysis Plan | |
| Study alias & e-track number(s): V59 77 (205352) | |
| Version: 1 | Date: 19-09-2016 |

GlaxoSmithKline

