2. STUDY DESIGN

This is a phase 3b, controlled, open-label, multi-center study to evaluate safety and immunogenicity of MenACWY-CRM after a single vaccination in healthy individuals who were vaccinated with Menveo or Menactra 4 to 6 years before and in vaccine-naïve individuals.

Study population: Approximately 700 healthy subjects 15 through 55 years of age will be enrolled in the study.

Duration of the study: The duration of this study is approximately 6 months per subject.

Written informed consent and, as applicable according to local guidelines, written assent will be obtained before conducting any study-specific procedures.

Vaccination schedule: All subjects will receive a single dose of MenACWY-CRM at Day 1.

Study groups:

Group Menveo-Menveo: approximately 300 subjects, who were vaccinated with a single dose of Menveo 4 to 6 years before, will receive one dose of MenACWY-CRM.

Group Menactra-Menveo: approximately 300 subjects, who were vaccinated with a single dose of Menactra 4 to 6 years before, will receive one dose of MenACWY-CRM.

Group Naïve: approximately 100 subjects equally enrolled across all clinical sites, who have not received any meningococcal vaccination, will receive one dose of MenACWY-CRM.

Randomization / Stratification:

| Statistical Analysis Plan | |  GSK GlaxoSmithKline |
|--|------------------|---|
| Study alias & e-track number(s): V59_77 (205352) | Version: 1 | |
| | Date: 19-09-2016 | |

Within each study group, subjects will be randomized into one of two different blood draw schedules according to a 1:1 ratio, described as follows:

- Subjects getting blood draws at Day 1, Day 4 and Day 29.
- Subjects getting blood draws at Day 1, Day 6 and Day 29.

Table 2-1: Schematic diagram of the V59_77 study groups

| Vaccine History | Vaccination in current study | Blood draw schedule |
|------------------------|------------------------------|---------------------------------|
| Menveo N=300 | Menveo | Blood draw Day 1, 4, 29 (N=150) |
| | | Blood draw Day 1, 6, 29 (N=150) |
| Menactra N=300 | Menveo | Blood draw Day 1, 4, 29 (N=150) |
| | | Blood draw Day 1, 6, 29 (N=150) |
| Vaccine-Naive N=100 | Menveo | Blood draw Day 1, 4, 29 (N=50) |
| | | Blood draw Day 1, 6, 29 (N=50) |

Blinding: open-label study.

Blood samples: Three (3) blood samples of approximately 10 mL each will be collected according to the blood draw schedule in Table 2-1.

Data collection: Electronic Case Report Form (eCRF).

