6.3.2. Additional considerations

Using the PPS (Day 29), the analyses of the primary objectives will be replicated by sex and race.

All sensitivity analyses will be performed on the PPS.

Reverse Cumulative Distributions Curves of hSBA Titers against *N. Meningitidis* serogroups A, C, W and Y will be produced at Days 1, 4, 6 and 29 for all study groups (Menveo-Menveo, Menactra-Menveo and the Naïve) on both the PPS and the FAS.

The adjusted ratio of GMTs, obtained from ANCOVA models including pre-vaccination titer as factors in the model, will be only computed as secondary analyses. The group titers of naïve subjects will be anyway always summarized without any adjustment (i.e. unadjusted GMTs and percentages).

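### The adjusted comparisons between non-randomised groups use pre-vaccination titer as their only covariate, so no planned between-group estimate corrects for age or sex

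*SAP*

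**What the plan says.** **Allocation.** SAP section 2 forms the three groups by vaccine history: "Within each study group, subjects will be randomized into one of two different blood draw schedules according to a 1:1 ratio". Protocol 5.1.4.2 says that the minimisation takes previous vaccination status into account and names no other factor.

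**Purpose of adjustment.** SAP 6.3.1 says that comparisons of percentages and GMT ratios will include "adjusted estimates from regression models to account for potential baseline imbalance between study groups".

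**Covariates.** For GMT ratios, an "adjusted ratio of GMTs will be obtained from ANCOVA models including pre-vaccination titer as factors in the model". For seroresponse and for titers of at least 8 and at least 16, "the difference in percentages will also be obtained from a log-linear model adjusting for pre-vaccination titer". Protocol 8.4.3.3.3 names the same covariate and, for the log-linear model, refers to the SAP for technical detail. The SAP adds none.

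**Status.** Under SAP 6.3.2 the adjusted GMT ratios "will be only computed as secondary analyses", and "All sensitivity analyses will be performed on the PPS". The same section adds that naive-group titers are in any case summarised unadjusted.

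**Age and sex elsewhere.** Sex enters the immunogenicity analyses only because "the analyses of the primary objectives will be replicated by sex and race". Age appears only in the by-group demographic summaries (SAP 6.1.1).

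**The concern.** The stated aim is to handle baseline imbalance between groups that were not randomised. The chosen covariate cannot do that for the primed-versus-naive contrasts. The Day 1 titer of a primed subject is partly produced by the earlier vaccination, and it is the outcome of secondary objective 2 (persistence). Conditioning on it asks how responses compare at equal starting titer. That is a legitimate question, but it is not a correction for who the subjects are.

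Age similarity is not secured elsewhere. The protocol synopsis says that naive subjects should be comparable in age to the primed groups. Protocol 3.1 and SAP section 2 do not repeat this, and no entry or allocation rule enforces it. Subjects may be up to 55 years old. Priming at any age from 11 qualifies, so the primed subjects could also be the older ones, and the direction of any imbalance is open.

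At stake is the use of the naive arm: the comparison of booster with primary response (Protocol 1.2) and of persistence with naturally acquired levels (secondary objective 2). Imbalance would show in the demographic tables, but no between-group estimate would take it into account.

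**Working it through.** No figure in the documents depends on the covariate choice, so there is none to reproduce.

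**1. Which estimates have no age or sex term.** There are 4 contrasts: each primed group versus naive, pooled versus naive, and primed versus primed.

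- Adjusted GMT ratios after vaccination: 4 contrasts × 4 serogroups × 3 days = 48 per analysis set, of which 3 × 4 × 3 = 36 are primed versus naive.
- Adjusted percentage differences (seroresponse, ≥8, ≥16): 48 × 3 = 144 on the PPS, of which 36 × 3 = 108 are primed versus naive.

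The 36 and 108 depend on the SAP 6.3.2 sentence about naive titers. If it covers only group summaries, they stand. If it also rules out adjusted naive contrasts, 48 − 36 = 12 ratios and 144 − 108 = 36 differences remain, all primed versus primed, and the naive contrasts have no adjusted estimate at all. On either reading, none corrects for age or sex.

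**2. Possible size of an age effect (all inputs assumed).** Shift in a GMT ratio = 10^(slope × age gap), in either direction.

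| Decline, log10 per year | Age gap, years | Fold shift |
|---|---|---|
| 0.005 | 2 | 10^0.01 = 1.02 |
| 0.01 | 5 | 10^0.05 = 1.12 |
| 0.02 | 10 | 10^0.20 = 1.58 |

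**3. Against sampling error.** Pooled versus naive at Day 29, with 540 and 90 evaluable (600 and 100 less the planned 10% dropout) and an assumed SD of 0.5 log10: the 95% half-width is 1.96 × 0.5 × √(1/540 + 1/90) = 0.1116 log10, or 1.29-fold. The age shift exceeds this only for gaps above 0.1116/slope, which is 22.3, 11.2 and 5.6 years at slopes of 0.005, 0.01 and 0.02. At Day 4 or 6 (270 versus 45) the half-width is at least 1.44-fold.

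**4. Effect of conditioning on Day 1 titer (assumed inputs).** The primed/naive ratio falls by 10^(baseline gap × post-on-pre slope): 10^(0.2 × 0.2) = 1.10, 10^(0.4 × 0.3) = 1.32, 10^(0.6 × 0.5) = 2.00.

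**5. Both together.** Simulation at the middle inputs (1,000 runs, true total ratio 4.17):

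| Naive group | Unadjusted | Titer only | Age + sex |
|---|---|---|---|
| 5 years older | 4.68 | 3.55 | 4.16 |
| 5 years younger | 3.72 | 2.82 | 4.19 |

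The arithmetic agrees: 4.17 × 1.12 ≈ 4.68, and 4.17/1.32 × 1.12 ≈ 3.55. Titer adjustment leaves the age shift in place and moves the estimate to a different target.

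**6. Day 1 wording.** GMT ratios are listed "at each of Visit Day 1 (Persistence), Day 4, Day 6 and Day 29", and the adjustment sentence that follows names no days. The paragraph on titers of at least 8 and 16 has the same gap; the seroresponse paragraph covers only Days 4, 6 and 29. If the ANCOVA were run at Day 1, outcome and covariate would be the same variable. In a simulated check the unadjusted ratio of 2.14 became 1.00, with zero residual variance.

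**The case against.** The best reply is that little depends on this. SAP section 7 makes all comparisons outside the primary objective descriptive. Secondary immunogenicity objectives have no formal tests and no success criteria. The titer-adjusted results have secondary or sensitivity status and stand beside unadjusted ones. Imbalance is hypothetical and would be visible in the demographic tables. The two primed groups share the same age and interval criteria, so the documents give no structural reason for them to differ in age. The mid-range age effect is smaller than the confidence interval half-width, and no figure is offered for sex. All of this stands, and it limits the weight of the point. It does not supply an estimate that does what SAP 6.3.1 says adjustment is for.

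A reader might infer more than the documents support:

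- **That the SAP orders a self-adjusted Day 1 ratio.** It does not. Adjusting for a pre-vaccination value presupposes a later outcome, and a perfect fit would be noticed. The missing day limit is a wording gap.
- **That a fixed number of primed-versus-naive outputs is affected.** The SAP 6.3.2 sentence on naive titers leaves this unclear.
- **That confounding is shown.** The age gap, the slope and the SD are all assumed.
- **That dropping covariates is an error.** The file also contains superseded protocol versions whose models named center, one of them with age group. That difference is background only.

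**Conclusion.** The point holds as a limited one. Groups are not randomised, adjustment is meant to address imbalance, and every adjusted between-group model names pre-vaccination titer alone. Against naive subjects that gives a contrast conditional on a consequence of priming, and no planned between-group estimate corrects for age or sex.

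The specification gap is certain from the text; its numerical consequence is not. The 1.02- to 1.58-fold range for age and the 1.10- to 2.00-fold range for conditioning on titer rest wholly on assumed inputs, and at middle values the age effect lies within sampling error. The primary tests compare single-group seroresponse rates with 75%, use no covariates and are unaffected. This is a cheap improvement worth making before analysis, because covariates chosen after the results are seen are less credible.

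**What to change.** In SAP 6.3.1:

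1. Keep all unadjusted estimates.
2. Add one adjusted model with age (continuous) and sex for between-group GMT ratios and percentage differences at Days 1, 4, 6 and 29.
3. Report titer-adjusted primed-versus-naive results as conditional on Day 1 titer, and say which of them are produced in view of the SAP 6.3.2 sentence on naive titers.
4. As a minor clarification, state that titer adjustment applies only to Days 4, 6 and 29.
5. Record the added model in SAP section 9, which currently lists no changes; the protocol names the same single covariate.

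**Cost.** One extra descriptive model per endpoint. Date of birth and sex are already collected at screening (Protocol 5.1.2). Some precision is lost. For a 5-year age gap, age alone multiplies the SE of the pooled-versus-naive contrast by about √(1 + 5² × (540/630) × (90/630)/s²), which is 1.02 at an assumed age SD s of 8 years and 1.09 at 4 years. Simulation with age and sex together gave 1.03 to 1.09, so about 3% to 9%. If the age ranges barely overlap, the age-adjusted estimate rests on extrapolation; the by-group age table would show this.

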6.3.2. Additional considerations

Using the PPS (Day 29), the analyses of the primary objectives will be replicated by sex and race.

All sensitivity analyses will be performed on the PPS.

Reverse Cumulative Distributions Curves of hSBA Titers against *N. Meningitidis* serogroups A, C, W and Y will be produced at Days 1, 4, 6 and 29 for all study groups (Menveo-Menveo, Menactra-Menveo and the Naïve) on both the PPS and the FAS.

The adjusted ratio of GMTs, obtained from ANCOVA models including pre-vaccination titer as factors in the model, will be only computed as secondary analyses. The group titers of naïve subjects will be anyway always summarized without any adjustment (i.e. unadjusted GMTs and percentages).

6.4. Analysis of safety

6.4.1. Analysis of safety planned in the protocol

Analyses of solicited adverse events - and other solicited reactions - and unsolicited adverse events will be performed on the relevant safety sets.

For unsolicited adverse events, the entire study period will be divided into the following intervals: onset within 30 minutes after vaccination, onset within 28 days after vaccination; and from Day 1 through Day 181. For solicited adverse events, the solicited study period will be divided into intervals: from 6 hours through day 3; from day 4 through day 7; and from 6 hours through day 7.

No imputation methods will be used to address missing safety data.

Summaries of safety will be presented using frequencies and percentages within each study group. No statistical comparisons among the study groups with respect to any of the safety parameters will be performed.

| | |
|--|------------------|
| Statistical Analysis Plan | |
| Study alias & e-track number(s): V59 77 (205352) | |
| Version: 1 | Date: 19-09-2016 |

Analysis of Solicited Local, Systemic and Other Adverse Events

All solicited adverse events will be summarized according to defined severity grading scales.

Frequencies and percentages of subjects experiencing each adverse event will be presented for each symptom severity. Summary tables showing the occurrence of any local or systemic adverse event overall and at each time point will also be presented.

Post-vaccination solicited adverse events reported from Day 1 to Day 7 will be summarized for the intervals Day 1 (6 hours) – Day 3, Days 4-7, Day 1 (6 hours) – Day 7 by maximal severity and by study group. Separate analyses will be performed for solicited AEs reported 30 minutes after vaccination. The severity of solicited local adverse events, including injection-site erythema and induration, will be categorized based on linear measurement: None (0-24 mm), Mild (25-50 mm), Moderate (51-100 mm), Severe (> 100mm).

Injection site pain and systemic reactions, including fatigue, headache, myalgia, arthralgia, chills, nausea, loss of appetite, occurring up to 7 days after each vaccination will be summarized according to “mild”, “moderate” or “severe”.

Each solicited local and systemic adverse event will also be further summarized as “none” versus “any”.

Use of antipyretics and analgesics will be summarized by frequency, by type of use (prophylactic versus treatment) and percentage of subjects reporting use.

Body temperature will be summarized separately according to the 3 schemes described below and will be broken down according to route of measurement:

- by 0.5 °C increments from 36.0°C up to ≥40°C;
- by 1°C increments: <36.0, 36.0-36.9, 37.0-37.9, 38.0-38.9, 39.0-39.9, ≥40°C;
- According to different cut-offs (< versus ≥): 38.0, 38.5, 39.0, 39.5, 40.0°C.

Statistical Analysis Plan

| | | |
|--|------------|------------------|
| Study alias & e-track number(s): V59 77 (205352) | Version: 1 | Date: 19-09-2016 |
|--|------------|------------------|

 GSK GlaxoSmithKline

Analysis of Unsolicited Adverse Events

This analysis applies to all adverse events occurring during the study, judged either as probably related, possibly related, or not related to vaccination by the investigator, recorded in AE CRF, with a start date on or after the date of first vaccination. AE starting prior to the first vaccination will only be listed. The original verbatim terms used by investigators to identify adverse events in the CRFs will be mapped to preferred terms using the MedDRA dictionary. The adverse events will then be grouped by MedDRA preferred terms into frequency tables according to system organ class (SOC).

All reported adverse events, as well as adverse events judged by the investigator as at least possibly related to study vaccine, will be summarized according to SOC and preferred term within SOC. These summaries will be presented by study group and by interval of study observation. When an adverse event occurs more than once for a subject, the maximal severity and strongest relationship to the vaccine will be counted.

Separate summaries will be produced for the following categories:

- Adverse events that are possibly or probably related to vaccine
- Unsolicited AEs reported within 30 minutes after vaccination
- Unsolicited AEs reported within 29 days after vaccination
- Adverse events leading to withdrawal
- Adverse events leading to a medically attended visit
- Serious adverse events

Data listings of all adverse events will be provided by subject. In addition, adverse events in the categories above will be provided as listed data.

